**8.2.1.b. Informed consent.** Eligible participants will complete standard consent documentation. Prior to the volunteer being asked any question about his/her health, the volunteer will be given a consent form to read. The research assistant will go over it in detail with the volunteer. After a physician investigator answers any questions the volunteer may have concerning the study, he/she will be asked to provide their informed consent to the licensed physician investigator. If enrolled in the study, consent to communicate with their other clinicians will be obtained. Clinicians will be notified of their patients' enrollment in the study, thus allowing them to carefully monitor for changes in mood while they are undergoing treatment to stop use of cannabis.

**8.2.1.c. Randomization.** Participants will be stratified according to their self-reported frequency of cannabis use in the past 30 days: 1) daily use; and 2) non-daily use. The stratification procedure will guard against the possibility that one of the experimental conditions (i.e., nabilone or placebo) will be overrepresented by daily users, while non-daily users will predominantly be randomized into the other condition.

**8.2.1.d. Availability and Flow of Subjects into Treatment.** We plan to screen 120 participants in the course of 20 months to achieve our desired sample size.

**8.2.1.e. Study Visits.** Participants will come to the clinic twice a week. One visit will include a medical visit (dispensing of pills and Medical Management; see Sections 8.3.1.b, 8.3.2) and research assessments, including a urine screen (see Section 8.5.2.a and **Table 8.2**). The other visit will consist only of a urine screen (see Section 8.5.2.a). After the 10-week treatment period, participants will have 1 follow-up assessment visit at 14 weeks. During weeks 11, 12, and 13 participants will have 1 weekly Diary/Actiwatch visit to hand in their daily diaries, have their Actiwatch data downloaded, and provide a urine sample.

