**8.3.1.b. Procedures for Dispensing Medication.**

Subjects will be randomized to receive either placebo or nabilone. [name] or the research assistants will present 7 day prescriptions to the McLean pharmacy and the subject will receive blister packs containing 1 week of medication or placebo, separated into daily doses. Subjects will be asked to return unused pills at each weekly medical visit; study staff will then perform a pill count for the study record. All groups will receive capsules following the same schedule: 4 capsules twice daily for 10 weeks. Each capsule will contain either nabilone or placebo, and riboflavin 25 mg (to help assess compliance). Subjects in the nabilone group will take 1 mg of nabilone at bedtime for 1 week, then increase to 1 mg of nabilone twice daily (between 7:00-9:00 a.m. and 9:00-11:00 p.m.) for 1 week, then 2 mg nabilone twice daily for 1 week, then 3 mg nabilone twice daily for 6 weeks before tapering the medication over the final 1 week by taking 2 mg nabilone twice daily for 2 days, then 1 mg twice daily for 2 days, then 1 mg at bedtime for 3 days before stopping. This schedule is designed to maximize the time spent at the maximum dose. Subjects will be assessed for side effects prior to each dosing increase and the study physician will decide if increasing the dose as scheduled is appropriate.

In order to monitor potential side effects from the initial dose of nabilone or dose increases, participants will be observed at the laboratory facility for 3 hours following the following the second dose of the day in weeks 1, 2, 3, and 4. Participants will come into the Behavioral Psychopharmacology Research Laboratory in the evenings for monitoring by a research assistant and a study physician. This observation period is follows the SAMHSA guidelines for induction of buprenorphine, another agonist pharmacotherapy (CSAT 2004). Participants will remain in the natural settings laboratory for 3 hours while having vital signs taken every 30 minutes. Participants will be allowed to leave the facility after being cleared by a study physician. Participants will be allowed to leave the facility if they have 1) pulse rate less than 120 beats per minute; 2) blood pressure less than 140/90.

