
**8.5.3. Mood and Impulsivity Assessments.** We will monitor participants' mood throughout the study using 3 assessments. The Beck Anxiety Inventory (BAI) is a 21-

**McLean Hospital Application to the Institutional Review Board (IRB)  
Nabilone for Cannabis Dependence Detailed Protocol**

item self-report measure that can be used to assess the severity of anxiety. The Quick Inventory of Depressive Symptomatology (QIDS-SR) is a short self-report questionnaire for depressive symptoms used successfully in the STAR\*D project. The Positive and Negative Affect Scale (PANAS) is a 20-item self-report scale in which mood variables are rated by participants on a 1-5 scale. The Barratt Impulsiveness Scale (BIS-11) is a commonly used tool to measure impulsivity in various neuropsychological disorders as well as in substance abuse. Three dimensions can be assessed using this scale, which include Cognitive Impulsivity, Motor Impulsivity, and Non-planning Impulsivity.

**Table 8.1** Schedule of Measures

Measure	Baseline	Weekly	Weeks 4 &10	Week 14
Diagnostic Assessment				
1. Structured Clinical Interview for DSM-IV a	X			
Drug and Alcohol Assessment				
2. Quantitative Urine Toxicological Analysis b	X	X b	X	X
3. Addiction Severity Index	X		X	X
4. Drug and Alcohol Use Questionnaire	X			
5. Weekly Drug and Alcohol Use Inventory	X	X	X	X
6. Marijuana Goals Questionnaire	X			
7. Marijuana Craving Questionnaire	X	X	X	X
8. Marijuana Withdrawal Checklist	X	X	X	X
9. Marijuana Perceptions of Risk and Experiences	X		X	X
Mood and Impulsivity Assessment				
10. Quick Inventory of Depressive Symptomatology	X		X	X
11. Beck Anxiety Inventory	X		X	X
12. Positive and Negative Affect Scale	X		X	X
13. Barratt Impulsiveness Scale	X		X	X
Medical & Safety Assessment (medical visits)				
14. Physical examination	X			X
15. ECG	X			X
16. Urine pregnancy test	X		X	X
17. Laboratory tests c	X			X
18. Adverse Events & Side Effects	X	X		X
19. Columbia Suicide Severity Rating Scale	X	X	X	X

aFull SCID at baseline

bTwice a week during treatment;

cTests include urinalysis, liver function tests, electrolytes, complete blood count, & blood chemistries

**8.6. Medication Adherence Assessment.** The proposed studies involve chronic administration of medication given under double-blind conditions. Three methods of

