**8.9. Statistical Analysis**

The primary data analysis will be an intent-to-treat analysis, which includes all randomized participants. Of note, every attempt will be made to continue assessing participants even if they drop out of treatment. In addition, we will replicate all analyses with the completers only. The primary and secondary outcome variables are intended to explore various aspects of response to therapy and to help define a clinically meaningful response. The primary outcome measures, Actiwatch-scores, daily diaries, TLFB self-report data, in addition to quantitative urinary THC metabolites, have been chosen for their ability to indicate daily use of cannabis by relying on self-report of use.

Specifically, for assessing the effect of nabilone on cannabis use patterns, we propose to use the generalized estimating equations (GEE) approach to longitudinal analysis, appropriately accounting for the positive correlation among repeated urine screen assessments within the same individual.

Analyses of secondary substance use outcomes will focus on the number of days of cannabis use and of any substance use (and conversely, days of abstinence) during treatment and post-treatment follow-up. In addition, we will also examine the ASI Drug and Alcohol composite scores. Frequency of days of cannabis use (and any substance use and days of abstinence) will be analyzed via a log-linear (or Poisson) regression model, controlling for pre-treatment frequency of days of cannabis use. Although log-linear regression methods are considered appropriate for the analysis of count or frequency data, in many biomedical applications, count data have variability that far exceeds that predicted by the Poisson distribution; we expect that days of cannabis use (and any substance use and days of abstinence) will not be an exception. Linear mixed effects models will be used to examine the effect of treatment group on changes in the ASI Drug and Alcohol composite scores during treatment and post-treatment follow-up assessments (as determined by the group-by-time interaction in the linear mixed effects regression models). The linear mixed effects model will include random intercepts and slopes to appropriately account for correlation among repeated measures and heterogeneity of variance over time; the model will be fit using PROC MIXED in SAS.

**McLean Hospital Application to the Institutional Review Board (IRB)  
Nabilone for Cannabis Dependence Detailed Protocol**

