In secondary analyses of mood outcomes, mood episodes will be assessed during treatment and post-treatment follow-up, using the QIDS, BAI, and PANAS; changes in risk of mood episodes during treatment and post-treatment follow-up assessments will be analyzed via a logistic regression model (similar to the logistic model above) that will be fit using the GEE approach (as implemented in PROC GENMOD in SAS) to account for correlation among repeated binary outcomes on the same individual. To examine the effect of nabilone on changes in risk for mood episodes during treatment and post-treatment follow-up, the logistic regression model will include the effects of treatment condition and the baseline measure of the outcome.

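### The mood-episode GEE in 8.9 lists only treatment and baseline, so it gives one odds ratio across on-drug and off-drug visits and cannot show whether the effect differs between the two periods the plan names

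*Combined protocol and SAP*

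**What the plan says.** Section 8.9 says that "changes in risk of mood episodes during treatment and post-treatment follow-up assessments" will be analysed with a logistic GEE in PROC GENMOD, using the QIDS, BAI and PANAS. The stated purpose is to examine nabilone's effect on changes in that risk over both periods. For content, "the logistic regression model will include the effects of treatment condition and the baseline measure of the outcome". The model is introduced as a "logistic regression model (similar to the logistic model above"), but no logistic model is written out earlier in 8.9. The nearest candidate is the urine-screen GEE, for which no link, covariates or time terms are given.

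In the same section, the linear mixed model for the ASI composites covers the same two periods and does state how change is judged: "as determined by the group-by-time interaction in the linear mixed effects regression models".

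Section 8.5.3 says the trial will monitor "mood throughout the study using 3 assessments". Table 8.1 marks those three scales at baseline, weeks 4 and 10, and week 14, with the weekly column blank. On follow-up, 8.2.1.e says "participants will have 1 follow-up assessment visit at 14 weeks"; the visits at weeks 11, 12 and 13 are for diaries, Actiwatch download and urine. On dosing, 8.3.1.b gives three one-week steps, "then 3 mg nabilone twice daily for 6 weeks before tapering the medication over the final 1 week".

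**The concern.** The sentence asks a two-period question, and the listed terms answer a one-period question. With only treatment and baseline in the linear predictor, the treatment log odds ratio is constrained to be the same at every visit. One of the three post-baseline visits is off drug.

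If nabilone alters mood-episode risk only while it is taken, the single odds ratio lies closer to 1 than the on-treatment effect. If risk moves the other way after the drug is stopped, the two effects partly offset each other and a reader would see little. In either case the output cannot show whether the treatment and follow-up periods differ. An agonist that is tapered and stopped gives a reason to look at the two periods separately, and the plan itself names both.

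**Working it through.** The plan states no odds ratio, event rate or power for mood episodes, so there is no figure of its own to reproduce.

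**1. Calendar (8.3.1.b, 8.2.1.e, Table 8.1).** Dosing lasts 1 + 1 + 1 + 6 + 1 = 10 weeks, and the last week is the taper (2 + 2 + 3 = 7 days). Week 14 is 14 - 10 = 4 weeks after dosing ends. Of three post-baseline mood visits, two fall in the treatment period (weeks 4 and 10) and one after it (week 14).

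**2. What the listed model estimates.** Take equal weight for the three visits, a constant placebo risk p, visit odds ratios OR_k, and no baseline adjustment.

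- Nabilone risk at visit k: q_k = p·OR_k / (1 - p + p·OR_k).
- Pooled OR = [q̄ / (1 - q̄)] / [p / (1 - p)], where q̄ is the mean of the three q_k.

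Worked case: p = 0.50 and ORs 0.5, 0.5, 2. Then q = 0.333, 0.333, 0.667, q̄ = 0.444, and the pooled OR is 0.444/0.556 = 0.80.

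| Assumed true ORs (weeks 4, 10, 14) | Pooled OR, p = 10% | Pooled OR, p = 50% |
|---|---|---|
| 0.5, 0.5, 0.5 | 0.50 | 0.50 |
| 0.5, 0.5, 1 | 0.66 | 0.64 |
| 0.5, 0.5, 2 | 0.95 | 0.80 |

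As a share of the on-treatment log odds ratio, ln(pooled OR)/ln(0.5), the second row is 60% to 65% and the third is 7% to 32%. The p and OR values are assumptions.

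**3. Same question by simulation.** In 300 simulated trials (30 per arm as in 8.2, assumed placebo risk 30%, ORs 0.5, 0.5, 2), the model with treatment and baseline gave a median treatment OR of 0.82. Adding period and treatment-by-period gave medians of 0.42 on treatment and 2.20 at week 14. These are baseline-adjusted, so they lie a little further from 1 than 0.5 and 2. The treatment-by-period term reached p < 0.05 in 67% of trials, for a fourfold ratio of odds ratios.

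**4. Precision cost of separating the periods.** On a linear scale with within-person correlation r:

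- SE(on treatment)/SE(pooled) = sqrt{[(1 + r)/2] / [(1 + 2r)/3]}, which is 1.10, 1.06 and 1.03 at r = 0.3, 0.5 and 0.7.
- SE(week 14)/SE(pooled) = sqrt[3/(1 + 2r)], which is 1.37, 1.22 and 1.12.

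Simulated logistic GEEs cost more. The settings were 30 per arm, 120 trials per setting, risks of 20% vs 40% or 30% vs 50% at all three visits, and latent correlation 0.3 to 0.7. Median ratios were 1.09-1.17 on treatment and 1.32-1.55 at week 14.

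**5. Sparse cells.** Assume placebo risk 10%, OR 0.5 and 30 per arm. The nabilone risk is 0.05/0.95 = 5.26%. The chance that at least one arm has no events at week 14 is 1 - (1 - 0.90^30)(1 - 0.9474^30) = 1 - 0.958 × 0.802 = 23%. At 5% placebo risk the same sum gives 57%. If every visit has its own treatment effect, the chance of at least one empty arm-by-visit cell is about half at 10% risk and 86-91% at 5%. A two-period model is therefore safer here than a three-visit one.

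**The case against.** **Will include is not the same as will include only.** The text also speaks of changes over two periods and points to another model, so it may be an abbreviated description, or one fit per period may have been meant. A reader might infer that the plan has deliberately ruled out time terms; the documents do not support that. What stands is narrower: these are the only terms listed, nothing elsewhere in 8.9 supplies others, and an analyst following the text would fit the pooled model.

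**The size is hypothetical.** This stands. A reader might infer a fixed loss, such as one third because one visit in three is off drug. On the risk-difference scale, with equal effects at weeks 4 and 10 and none at week 14, the share is indeed 2/3 = 67%. The plan's estimate is an odds ratio, however, and there the share depends on event rates. Nor do the documents support any particular effect after stopping, including a rebound.

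**Dose is a side issue.** A reader might want to classify visits by dose, since weeks 4 and 10 fall near a dose step and the taper, and assessments share the visit at which pills are dispensed (8.2.1.e). That is a separate exposure question and does not bear on the missing term.

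**Mood episode is not defined.** The plan gives no cut-off on the three scales and no rule for combining them. This gap is real, and adding a period term does not close it.

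**Priority.** Mood is in neither Specific Aim, the study is a Stage 1 pilot, and a time-averaged effect is a legitimate and more precise target. A reader might infer that participant safety rests on this model. It does not: Table 8.1 schedules the C-SSRS and adverse events weekly.

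**Conclusion.** The point holds as a cheap improvement. That the listed terms cannot separate the two periods follows from the text alone and needs no assumption about rates. It is more than missing detail, because following the listed terms gives a poorer answer to the plan's own question, and the ASI model beside it already uses a group-by-time term.

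The amount of blending is unknown. There is none if the effect persists after stopping. Under the assumed values above, an on-treatment odds ratio of 0.5 would be reported as about 0.64-0.66 if the effect is gone at week 14, and as about 0.80-0.95 if it reverses to 2. These figures assume equal effects at weeks 4 and 10, constant placebo risk and equal attendance; lower attendance at week 14 would give that visit less weight. The consequence is confined to the interpretation of a secondary analysis and does not touch the primary result.

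**What to change.** Replace the model sentence in 8.9 with wording such as: *The logistic GEE will include treatment condition, period (on treatment = weeks 4 and 10; post-treatment = week 14), treatment-by-period and the baseline measure of the outcome. The treatment odds ratio will be reported for each period, with the ratio of the two, each with a 95% confidence interval. If an arm has no events in a period, exact risk differences will be given for each period.*

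Keep the pooled odds ratio as a supplement, since it is the more precise summary if the effect persists. Write out the logistic model referred to as above, or delete the reference.

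The cost is SAP wording and two model terms, with no new visits or data. The downside is wider intervals: standard errors about 9-17% larger on treatment and 32-55% larger at week 14 than the pooled one, under assumed event rates of 20-50%, with sparse cells possible at lower rates. With 30 per arm, the ratio between periods should be read as an estimate with its interval; a non-significant interaction would not show that the periods agree.

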**9. Human Subjects and Recruitment Strategies:**

9.1. Sample Size: In order to meet the target sample of 60 completers, we expect to recruit 120 participants, ages 18-45, and have 90 of them sign the informed consent form.

9.2. Advertising: Participants will be recruited via websites, newspaper advertisements, flyers on campus, and word-of-mouth. We will not specifically recruit participants from particular patient units at McLean. Participants may not be inpatients at McLean at the time of their participation in the study.

9.3. Inclusion criteria

1) Age range 18-45 years; 2) DSM-IV diagnosis of cannabis dependence, based on the Structured Clinical Interview for DSM-IV (SCID); 3) express a desire to quit cannabis use within the next 30 days; 4) have used cannabis on  $\geq 4$  days within the past 30 days (i.e., an average of  $\geq 1$  day per week); 5) for women of childbearing age, a negative pregnancy test at screening with agreement to use adequate contraception to prevent pregnancy and monthly pregnancy tests; 6) consent for us to communicate with their prescribing clinician; 7) furnish the names of 2 locators, who would assist study staff in locating them during the study period; 8) live close enough to McLean Hospital to attend study visits; 9) plan to stay in the Boston area for the next 3 months; and 10) are willing and able to sign informed consent.

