**8. Research and Design Methods:**

**8.1. Overview**

We will conduct a Stage 1 pilot feasibility study at McLean Hospital to develop a medication to treat cannabis dependence. (FIGURE 1) In a randomized, double-blind, placebo-controlled trial, 60 cannabis-dependent subjects ages 18-45 will receive medical management (MM) over a 10-week period, with half receiving nabilone treatment and half receiving placebo. Participants will receive either 6 mg nabilone or placebo in addition to medical management (MM) over a 10-week treatment period.

**McLean Hospital Application to the Institutional Review Board (IRB)  
Nabilone for Cannabis Dependence Detailed Protocol**

Following treatment completion, participants will have a follow-up visits at 11, 12, 13, and 14 weeks. Primary outcomes will include self-report of cannabis smoking and results of quantitative urine drug screens for cannabis. We also will assess craving and other marijuana withdrawal symptoms as secondary measures. Mixed models ANOVA will be used to analyze the data.

The protocol described in this document has been approved by the FDA under IND 107862 to [name].

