**8.2.1.g. Participant Payments**

Volunteers will receive a \$50 remuneration for attending the initial assessment interview and an additional \$50 for the baseline visit. They may earn \$25 for each urine sample given on a non-MM day in the first 5 weeks of treatment and then \$30 for each urine sample given on a non-MM day in the last 5 weeks of treatment, and they may earn \$50 for attending the follow-up assessment at 14 weeks. They may earn \$30.00 for each of three Actiwatch /Diary visits at weeks 11, 12, and 13 as well as \$50 for the final follow-up visit. Additionally they may receive a \$40 bonus for attending all follow-up visits and returning the Actiwatch. They may also receive a bonus of up to \$100 for successful

**McLean Hospital Application to the Institutional Review Board (IRB)  
Nabilone for Cannabis Dependence Detailed Protocol**

completion of their diaries. They may earn a total of \$705 for their participation in the study. Medication will be free. In special circumstances, a subject may receive up to \$50 in public transportation cards.

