**8.4. Safety Monitoring.** Nabilone has been shown to have a favorable safety profile; it has been well-tolerated in several clinical trials and no adverse events have been reported (Ware et al. 2008, Frank et al. 2008, Skrabek et al. 2008). Drug-drug interactions are not a major concern with nabilone because it does not induce cytochrome P450 3A4 isoenzymes and lacks significant 3A4 inhibitory effect (Nahas et al. 2002). Nonetheless, we will monitor safety through the standardized methods described above in the MM visits. We will have a low threshold for obtaining additional medical workup during the study if the subject reports medical symptoms. If a participant has a clinically significant laboratory or other medical abnormality that cannot be attributed to another cause, the participant's medication will be discontinued and the participant will be followed for research visits.

**McLean Hospital Application to the Institutional Review Board (IRB)  
Nabilone for Cannabis Dependence Detailed Protocol**

As discussed above in Section 8.2.i.a, the study physician will perform a physical examination and obtain an ECG at baseline and at 14 weeks. Laboratory data (urinalysis, blood chemistries, complete blood count, electrolytes, and liver function tests) will be done at baseline and at 14 weeks as well. Given that according to its labeling, nabilone should not be taken with alcohol, sedatives, hypnotics, or other psychoactive substances because they could potentiate the central nervous system effects of nabilone, urine toxicology and blood alcohol testing will be done weekly along with the twice weekly quantitative THC urine screens during treatment. Women of childbearing potential will have urine pregnancy tests weekly each time a urine sample is given in addition to pregnancy tests at weeks at 4, 10, and 14 weeks during treatment; women who become pregnant will have their medication discontinued and will be referred to an obstetrician; like all participants, they will still be followed for research visits.

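### The required 3-month stay in the area is 6–9 days shorter than the schedule to the week-14 visit, so people who already plan to leave before that visit can be enrolled

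*Combined protocol and SAP*

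**What the plan says.** Section 9.3, criterion 9, requires that participants "plan to stay in the Boston area for the next 3 months". It gives no starting point for the three months. No other criterion sets a length of stay: criterion 8 concerns living near enough to attend, and criterion 7 asks for two locators.

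The schedule is longer. Section 8.1 gives study drug or placebo "in addition to medical management (MM) over a 10-week treatment period" and then says "participants will have a follow-up visits at 11, 12, 13, and 14 weeks". Section 8.2.1.e separates these visits by content: "After the 10-week treatment period, participants will have 1 follow-up assessment visit at 14 weeks", whereas "During weeks 11, 12, and 13 participants will have 1 weekly Diary/Actiwatch visit to hand in their daily diaries", with an Actiwatch download and a urine sample.

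Section 8.2.1.g pays for screening and baseline as separate visits: "remuneration for attending the initial assessment interview and an additional \$50 for the baseline visit". The documents do not say how far apart they are.

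On safety, section 8.4 states that "the study physician will perform a physical examination and obtain an ECG at baseline and at 14 weeks", and it puts the laboratory tests at the same two times. Table 8.1 agrees.

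**The concern.** A length-of-stay criterion exists to keep out people who already know that they will be unavailable for part of follow-up. If it is shorter than the schedule, it does not do this for the last visit.

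That visit carries more than the other post-treatment contacts:

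- **Safety.** Week 14 is the only scheduled physical examination, ECG and laboratory panel after any exposure to study drug. A participant who misses it has baseline values and nothing scheduled to compare them with.
- **Secondary outcomes.** Section 8.9 analyses ASI composites and mood outcomes during treatment and post-treatment follow-up. In Table 8.1, week 14 is the only post-treatment time point for the ASI and the mood scales. Section 8.5.2.c gives the craving and withdrawal scales weekly during treatment and then only at the 14-week visit.
- **Completers.** Section 8.2 defines completers as those who complete all study procedures and sets a target of 60, from 90 who sign consent. Section 8.9 repeats every analysis in completers. Someone who leaves before week 14 and does not return cannot be counted as one.

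**Working it through.** **Inputs**

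- Required stay: 3 months (section 9.3, criterion 9).
- Treatment: 10 weeks (sections 8.1 and 8.2.1.e).
- Last visit: 14 weeks (sections 8.1 and 8.2.1.e).
- Interval from screening to treatment start: not stated. A range of 0–4 weeks is assumed here.

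**Step 1: reproduce the plan's timeline.** The dosing steps in section 8.3.1.b are 1 + 1 + 1 + 6 + 1 = 10 weeks, which matches the stated treatment period. Adding weeks 11–14 gives 10 + 4 = 14 weeks, and 14 × 7 = 98 days from treatment start.

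**Step 2: length of three months.** Counted from every start date over a four-year cycle, three calendar months last 89 to 92 days (mean 91.3), or 12.7 to 13.1 weeks.

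**Step 3: shortfall with no screening interval.** Shortfall = 98 − length of stay. This gives 98 − 92 = 6 days to 98 − 89 = 9 days.

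**Step 4: add a screening interval.** If the stay is counted from screening and treatment starts s days later, the shortfall for a visit on study day v is (v + s) − 92 to (v + s) − 89. Positive values mean that the visit falls after the required stay has ended.

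| Assumed interval s | Week 14 (day 98) | Week 13 (day 91) | Week 12 (day 84) | Week 10 (day 70) |
|---|---|---|---|---|
| 0 days | 6 to 9 | −1 to 2 | −8 to −5 | −22 to −19 |
| 7 days | 13 to 16 | 6 to 9 | −1 to 2 | −15 to −12 |
| 14 days | 20 to 23 | 13 to 16 | 6 to 9 | −8 to −5 |
| 21 days | 27 to 30 | 20 to 23 | 13 to 16 | −1 to 2 |
| 28 days | 34 to 37 | 27 to 30 | 20 to 23 | 6 to 9 |

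Week 14 is uncovered in every row. Week 13 is borderline with no interval and uncovered from one week on. Week 12 is uncovered from two weeks on. The end of treatment, and with it the twice-weekly urine outcome, stays covered until the interval reaches about three weeks.

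**Step 5: stay needed.** From treatment start, 98 days. From screening, with an assumed interval of 1–4 weeks, 98 + 7 = 105 to 98 + 28 = 126 days.

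**The case against.** The strongest reply is that criterion 9 sets a minimum intended stay, not a departure date. A reader might infer that people who just meet it are planned to be absent at week 14, or that their data are missing by design. The documents do not support that. Someone who intends to stay at least three months is not thereby intending to leave on day 91. Only a person who plans to move in the window between the end of the required stay and week 14 is affected, and only if that person does not come back. The documents give no figure for how many such people there are. This part of the reply stands.

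Other points also limit the matter:

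- Criterion 9 does not say that the three months run from screening. That is a plausible reading, but an inferred one, so any shortfall beyond 6–9 days is an assumption.
- No visit window is stated. If the visit could be held a week early, on day 91, and screening took no time, the gap would almost vanish (91 − 92 = −1 to 91 − 89 = 2 days). The plan does not provide for this.
- A reader might take week 14 to be the only contact after treatment. It is not: weeks 11–13 collect urine, diary and Actiwatch data. Adverse events and suicide risk are recorded weekly according to Table 8.1, so on-treatment safety monitoring does not depend on week 14.
- Section 8.2.1.g pays $50 for the week-14 visit and a $40 bonus for attending all follow-up visits and returning the Actiwatch. Section 8.9 commits to continued assessment of people who drop out of treatment.
- A screener who heard of a planned move could refuse entry under criterion 8. Its wording concerns distance, however, and it sets no length of stay.

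These provisions reduce the effect. None of them screens out a move planned for after month 3 and before week 14, and criterion 9 is the place where the plan meant to do that. Recruitment by campus flyers (section 9.2) makes people with fixed departure dates foreseeable, though not countable.

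**Conclusion.** The mismatch is real and the correction is worth making, but it is a modest point. Criterion 9 is 6–9 days too short for the plan's own schedule. This takes the week-14 visit as falling 14 completed weeks after treatment start and allows no screening time. It is 13–23 days too short if screening takes an assumed 1–2 weeks and the stay is counted from screening.

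The exposure is the loss, for an unknown and probably small number of people, of the one scheduled post-exposure examination, ECG and laboratory time point, the one full post-treatment assessment, and completer status. The on-treatment urine outcome is largely unaffected, and so are the data from weeks 11–13 if screening is short. Nothing here shows a bias in the primary treatment comparison. Confidence is high for the calendar arithmetic; the documents do not allow the number affected to be estimated.

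**What to change.** Reword criterion 9 so that the planned stay runs through the week-14 follow-up visit, instead of for a fixed three months. Tying it to the visit works whatever the screening interval turns out to be and removes the question of when the three months begin.

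A flat four months would be a blunter remedy. At about 4 × 365.25 / 12 = 122 days, it exceeds the certain need of 98 days by 122 − 98 = 24 days, and it could exclude people able to attend every visit.

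The cost is a one-line amendment and the exclusion of a few people who plan an earlier move. They are the people who could not have met the completer definition without returning for the visit.
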